#### Objective 2-5:

For objectives 2 to 5, SMD of each of the covariates for the comparison of drug users in the pre-RMM and post-RMM period as a measure of the impact of the profile of drug users. These covariates will include: duration and cumulative dose (objective 2), patient characteristics (objective 3) and line of treatment (objective 4). For patient characteristics, only conditions will be compared, with the assessment window set as any time prior to 1 day before the index date. For objective 5, covariates will include the proportion of patients diagnosed with meningioma during treatment, and the proportion of patients who discontinue or switch to alternative treatments (assessed separately).

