#### **Covariates for stratification:**

Covariates for stratification will vary across objectives and will include:

- Age group:
   10-17, 18-34, 35-49, 50-64, +65 years.
- Indication:

Non-HRT vs. HRT. Indication will be assessed using age as a proxy (non-HRT in women aged 10-49 years, HRT in women aged >50 years).

- Dose:
  - High- vs low- dose, for NOMAC or CMA only. For NOMAC, high doses will include amounts from 3.75mg to 5mg. For CMA, high doses will include amounts from 5mg to 10mg. Low doses will be any amounts less than those specified.
- WHO 5th ATC level codes:
  - For NOMAC or CMA only, if counts allow. For NOMAC codes included will be: G03AA14, G03DB04, G03FB12. For CMA, codes included will be: G03AA15, G03AB07, G03DB06, G03FB03.
- Time period:
  - Preintervention: from start date to October 2022; Postintervention: from February 2023 to study end.

See below which covariates apply according to each objective.

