Concomitant medications	Large-scale characterisation and pre-specified medications 	Binary	[-365, -31], [-30,-1], 0	IP, OP	RxNo rm		New users of drug classes of interest or progestogens (objective 3)
Time period	Preintervention: January 2010 (or study start) to October 2022 Postintervention: February 2023 to end of available data	Categorical	N/A	IP, OP	N/A	N/A	All.

<sup>1IP = inpatient, OP = outpatient

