## Objective 2:

Treatment duration will be reported for the first prescribed treatment. Duration will be derived from the start and end of the prescription.

Cumulative dose will be calculated considering all treatments containing NOMAC or CMA recorded during the study period. If two eras with different doses are separated by less than 30 days, the time between the two eras will be considered as exposed by the first era (Figure 1, first row). If two eras start at the same date, the overlapping period will be considered exposed by both.

[figure not shown]

Figure 1. Gap era joint mode

Cumulative dose and treatment duration will be calculated for all treatments initiated during the study period and occurring over one year before and after the intervention to compare time periods of equal duration. The pre-intervention period for comparison will span from October 2021 to September 2022,

Authors: [name], [name], [name], [name], [name]

Version: V4.0

Dissemination level: Public

the year prior the request for PRAC to review current evidence on NOMAC and CMA. The post-intervention period for comparison will span from February 2023 to January 2024. For databases with less available data (see Table 3) we will limit the comparison to 6 months (post-intervention: February to July 2023; pre-intervention: February to July 2022). Time periods for comparison will cover the same calendar months in case seasonality is detected.

NOMAC and CMA will be assessed separately. Results will be reported overall and stratified by study period (pre- vs. postintervention) and indication at first use (non-HRT vs. HRT).

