The amount of pre-intervention data to include for this analysis will be based on defining a valid counterfactual for the ITS analysis. Given the large amount data (12 years before the intervention), the range of pre-intervention data will be restricted to ensure the validity of the comparison (i.e. historical trends might differ from the most recent ones). To analyse the impact of restrictions adopted in 2022, analysis will be conducted using data from 1st January 2021 onwards. For NOMAC, the intervention adopted in 2018 will be assessed using data from 1st January 2017 onwards. Methodological considerations will be evaluated based on the visual assessment of the trends. This may include adjustments on the amount of pre-intervention data or the frequency of data points, if deemed necessary to support the analysis.

Results will be reported overall and stratified by dose (high- vs. low- dose products) and indication (non-HRT vs. HRT).

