#### A. Primary analysis

Hypothesis:	Objective 1: Not applicable, descriptive analysis.
	Objective 2: Cumulative dose and duration of treatments with NOMAC or CMA will be lower after the implementation of restrictions.
	Objective 3: The number of new users of NOMAC or CMA with prior history of meningioma will be reduced after the implementation of restrictions.
	Objective 4: The number of users initiating NOMAC or CMA as first-line treatment will be reduced after the implementation of restrictions.
	Objective 5: The number of discontinuations and switches from NOMAC or CMA to other drug classes will increase after the implementation of restrictions.
	Objective 6: The incidence of NOMAC or CMA will be reduced after the implementation of restrictions, especially for high-dose products. This reduction will not be observed for other drug classes of interest.
Exposure contrast:	Objective 1: Not applicable, descriptive analysis.
	Objective 2: Pre-intervention (1-year period) vs. Post-intervention (1-year period)
	Objective 3 to 6: Pre-intervention vs. Post-intervention
Outcome:	Objective 1: Incidence rates and prevalence of drug classes of interest
	Objective 2: Cumulative dose and treatment duration of NOMAC or CMA.

Authors: [name], [name], [name], [name], [name]

Version: V4.0

Dissemination level: Public

	Objective 3: Number and characteristics of users of drug classes of interest.
	Objective 4: Line of treatment when initiating NOMAC or CMA.
	Objective 5: Diagnosis with meningioma during treatment. Discontinuations and switches
	from treatments with NOMAC or CMA to others.
	Objective 6: Incidence rates of NOMAC or CMA.
	Drug classes of interest, NOMAC and CMA will be assessed separately.
Analytic software:	R
Model(s):	Objective 1: Not applicable, descriptive analysis.
	Objective 2 to 5: Standardised mean differences.
	Objective 6: Segmented regression (Poisson models).
Confounding adjustment method	
	Stratification.
Missing data methods	
	The absence of a record for a condition or medication will be considered as the absence of the disease or use of the medication.
Subgroup Analyses	
	Objective 1: Age groups, indication, study period. For NOMAC or CMA only: dose, WHO ATC 5 th level (if counts allow). A subgroup analysis will be performed restricting the study population to individuals with a prior history of meningioma.
	Objective 2: Study population, indication, study period.
	Objective 3: Study period.

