#### **Databases:**

In IQVIA LPD Belgium and IQVIA DA Germany, the observation period of the patients in these databases is calculated based on the last visit, observation or interaction of the patient with the health care system. This methodology impacts the individuals considered "at risk" for the different medicines of interest of the study (i.e., the individuals included in the denominator populations) during the latest months of available data from the latest data lock, where healthy and/or non-frequent users of the health care system will not be considered active. Consequently, the denominators that will be used to calculate the incident use of drugs in the population may present an artefactual decrease whilst the incident users will remain, incrementing the incidence and prevalence ratios. The presence of these artefacts will be considered when interpreting the results. However, this is likely to affect the amount of follow up available for the study. We expect that the data from the last 6 months may not accurately reflect actual figures of use and, therefore, will be excluded from the analysis for Objective 1 and 6.

Regarding the study period, NAJS will provide data from 2017 onwards only, as prior data might include information on duplicated patients. IQVIA LPD Belgium will provide data from 2012 onwards.

Since information on drug exposure end dates is unavailable in NAJS, treatment duration will not be inferred directly from the start and end dates of drug exposure. Instead, we will infer the treatment period using only the drug exposure start dates, assuming continuous drug exposure between consecutive start dates, if separated by less than 90 days. To account for the final prescription, we apply a 30-day window following the last recorded drug start date. This approach might lead to some uncertainty regarding the exact duration or cumulative dose prescribed.

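### Objective 4: the pre/post SMD sets all initiators since study start against a few post-RMM months with no calendar-time term, so any secular drift in first-line share enters the impact measure

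*Protocol*

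**What the plan says.** Protocol section 8.8 (Objective 2-5) names the pre/post standardised mean difference as the comparison: "SMD of each of the covariates for the comparison of drug users in the pre-RMM and post-RMM period as a measure of the impact". The sentence continues with a reference to the profile of drug users. Table 11 lists the model as "Objective 2 to 5: Standardised mean differences" and the contrast as "Objective 3 to 6: Pre-intervention vs. Post-intervention".

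The periods are set in section 8.6.3: "Preintervention: from start date to October 2022; Postintervention: from February 2023 to study end". Table 9 repeats this: "Preintervention: January 2010 (or study start) to October 2022". Section 11 moves the start for two databases: Belgium supplies data from 2012, and "NAJS will provide data from 2017 onwards only". The Objective 4 text in 8.8 sets no shorter window. It stratifies by period, dose and indication.

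Two other objectives are treated differently. For Objective 2, treatments are those "occurring over one year before and after the intervention to compare time periods of equal duration", with a six-month February-July 2022 versus 2023 alternative where data are short. For Objective 6, "the range of pre-intervention data will be restricted to ensure the validity of the comparison (i.e. historical trends might differ from the most recent ones", and data start in January 2021.

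**The concern.** Table 11 gives Objective 4 a directional hypothesis: fewer first-line starts after the restrictions. The pre/post SMD is the only planned measure of that contrast beyond the counts and proportions themselves. A single comparison of one long period with one short later period cannot separate a step at the intervention from a gradual change already under way. A falling first-line share would produce an SMD in the hypothesised direction with no RMM effect. A rising share could cancel a real fall. Not being used first-line is one of the central 2022 measures for high-dose products, so this comparison bears directly on the study question. The protocol acknowledges the hazard of a long pre-period for Objective 6 but does not carry the safeguard over, and section 11 does not mention secular trend for Objective 4.

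**Working it through.** The protocol gives no SMD value, threshold or sample size for Objective 4, so there is no figure of its own to reproduce. Two things can be checked: how far apart the compared periods lie, and what a given drift would do.

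**Inputs from the protocol.** Pre-period starts: 1 January 2010 (Germany), 2012 (Belgium), 2017 (NAJS). Pre-period end: 31 October 2022. Post-period start: 1 February 2023. Data locks (Table 3): 30 September, 31 December and 17 November 2023. Table 6 also requires 365 days of prior history. If data begin in 2012 and 2017, the first possible index dates in Belgium and NAJS move to about 2013 and 2018.

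**Assumptions, not in the protocol.** Linear drift of 1 percentage point per year (range 0.5 to 2), first-line share about 50%, initiations spread evenly over time, no RMM effect.

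**Step 1, distance between midpoints.**

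| Database | Pre midpoint | Post midpoint | Gap (years) |
|---|---|---|---|
| Germany | June 2016 | June 2023 | 7.0 |
| Belgium | June 2017 (Dec 2017 with history rule) | mid-July 2023 | 6.1 (5.6) |
| NAJS | Dec 2019 (June 2020 with history rule) | late June 2023 | 3.6 (3.1) |

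February-July 2022 versus February-July 2023 gives a gap of 1.0 year.

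**Step 2, spurious difference.** With linear drift and even initiation, difference = drift × gap. At 1 point per year this is 7.0 points in Germany, 5.6 to 6.1 in Belgium, 3.1 to 3.6 in NAJS, and 1.0 point with windows one year apart.

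**Step 3, SMD.** SMD = (p_post − p_pre) / √{[p_pre(1 − p_pre) + p_post(1 − p_post)] / 2}. Near a 50% share the denominator is about 0.5. Germany: 0.070 / 0.5 = 0.14. Absolute values:

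| Drift per year | Germany | Belgium | NAJS | Windows 1 year apart |
|---|---|---|---|---|
| 0.5 point | 0.07 | 0.06 | 0.03-0.04 | 0.01 |
| 1 point | 0.14 | 0.11-0.12 | 0.06-0.07 | 0.02 |
| 2 points | 0.28-0.29 | 0.23-0.25 | 0.12-0.14 | 0.04 |

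At 1 point per year, moving the share at November 2022 to 40% or 60% changes these by less than 0.01.

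**Step 4, opposite direction.** In Germany, a rise of 1 point per year adds 7.0 points between midpoints. A true fall of 7 points at the RMM then gives −7 + 7 = 0, and an SMD of about 0.

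**Step 5, a time term.** Fitting intercept, calendar time, post step and slope change to the drifting series with no RMM effect (Germany, 1 point per year downward) returned a slope of −0.01 per year, step 0 and slope change 0. The trend is separable once calendar time is in the model.

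**The case against.** The strongest reply is that Objectives 3 and 4 are worded as descriptive, that the quoted sentence goes on to speak of the profile of users rather than of the restrictions, and that estimating impact belongs to Objective 6. This stands in part: the protocol nowhere says that an Objective 4 SMD will be read causally. But sections 3 and 8.1 place the patient-level Objectives 2 to 5 under RMM effectiveness, and Table 11 attaches a directional hypothesis, so readers will take the SMD as evidence on the restriction.

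A reader might go further and infer that first-line share is in fact drifting, or that the plan would produce a false-positive finding at some stated rate. The documents support neither. They report no trend in first-line share, set no SMD cut-off and plan no significance test. Unequal look-back and the earlier NOMAC measures could each shift the baseline, but they are separate matters and this point does not rest on them.

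A reader might also apply the figures to Objective 3. They do not carry over. The Table 11 hypothesis there concerns prior meningioma, which is rare. For illustration, an assumed doubling from 0.1% to 0.2% gives an SMD of only 0.026. Section 8.7 expects adequate numbers for the SMDs in Objectives 3 to 5, and section 8.8 masks counts below 5, so a short window has a real cost for rare conditions.

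Two further points stand. Objective 2's equal windows are justified by equal duration and seasonality, not drift, so the protocol's own argument about trends comes from Objective 6 alone. Stratifying Objective 4 by dose and indication, together with the monthly incidence in Objective 1, makes some product-mix change visible, but neither shows the trend in first-line share.

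**Conclusion.** The point holds for Objective 4, as a cheap and worthwhile improvement. The full-period contrast is fixed by section 8.6.3 and Tables 9 and 11, not left open. The gaps of about 7.0 (Germany), 5.6-6.1 (Belgium) and 3.1-3.6 years (NAJS) follow from the stated dates and the even-initiation assumption. Later data locks would widen them. Whatever drift exists is multiplied by these gaps, instead of by about 1 year with matched windows. The SMD figures are illustrations that depend on the assumed drift and a share near 50%. They show what the design would absorb, not what it will find. For Objective 3 only a limited sensitivity analysis is supported.

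**What to change.** In section 8.8 and the Table 11 exposure contrast:

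- Base the Objective 4 pre/post SMD on initiators in equal-length windows of the same calendar months close to the intervention, for example February-July 2022 versus February-July 2023, longer where post data allow. Report it with its confidence interval, and keep the full pre-period for description.
- Report first-line share by calendar year before the RMM, and state that only a change beyond that trend is read as impact.
- State that a 2022 pre-window lies inside the referral (Appendix II: started 30/09/2021, PRAC recommendation 07/07/2022), so anticipatory change may bias towards no effect.
- For Objective 3, add the short-window SMD only as a sensitivity analysis for common conditions, because rare ones such as meningioma may fall below the minimum cell count of 5.

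This needs wording and a date filter of the kind Objective 2 already requires, and no new data. The price is precision. With SE ≈ √(1/n_pre + 1/n_post) and an assumed 300 post-period initiators, 300 in a matched pre-window give √(1/300 + 1/300) = 0.08. The full German pre-period, scaled by months (300 × 154/8 = 5,775), gives √(1/5,775 + 1/300) = 0.06.

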## 8.7 Study size

The expected number of patients exposed to NOMAC or CMA is expected to be roughly between 1,900 in NAJS and 16,800 in IQVIA DA Germany and between 2,4004 in IQVIA LPD Belgium and 173,900 in IQVIA

<sup>2Specify whether a diagnosis code is required to be in the primary position (main reason for encounter)

<sup>3 These will include: meningioma, obesity, diabetes mellitus, type 2 neurofibromatosis, asthma, autoimmune diseases, epilepsy, uterine fibroids, menopause/perimenopause, primary ovarian insufficiency, endometriosis, polycystic ovarian syndrome, menstrual disorders, neoplasm of the endometrium, neoplasm of the brain, neoplasm of the breast, cancer (any malignancy), hyperlipidaemia, hypertensive disorder, osteoporosis, venous thromboembolism.

<sup>4 These will include: progestogen and oestrogen combination products not containing NOMAC or CMA, progestogens that are pregnadien derivates not containing NOMAC or CMA, progestogen and oestrogen combination products not containing NOMAC or CMA, NOMAC, CMA, medroxyprogesterone, antidepressants, metformin, bisphosphonates, clonidine, gonadotropin releasing hormone antagonists and anti-androgens.

Authors: [name], [name], [name], [name], [name]

Version: V4.0

**Dissemination level:** Public

DA Germany, respectively. These counts were provided as part of the feasibility assessment and correspond to the entire source data, without restriction on age, sex or study period.

No specific sample size calculations have been performed. Given that meningioma is a rare tumour, we expect to have limited sample size in Objective 1, when restricting the population to individuals with prior history of meningioma. For Objective 3, 4 and 5, we expect an adequately large sample size to estimate Standardised Mean Differences (SMD) accurately. For Objective 2, this might be more limited as we will only consider users initiating treatment within a period of 6 to 12 months.

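### The pre/post contrasts of Objectives 2 to 5 rest on a point SMD without a confidence interval, and section 8.7 asserts an accuracy that was never estimated and is doubtful for the smallest Objective 4 cells

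*Protocol*

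**What the plan says.** Table 11 gives each of Objectives 2 to 5 a hypothesis with a direction. The one for line of treatment (Objective 4) reads "The number of users initiating NOMAC or CMA as first-line treatment will be reduced after the implementation of restrictions". The other three expect smaller doses and shorter treatment (Objective 2), fewer starters with a past meningioma (Objective 3), and more stopping and switching (Objective 5).

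The model row of the same table reads "Objective 2 to 5: Standardised mean differences". Table 1 lists the SMD among the main measures of effect, next to medians (Objective 2) and counts and proportions (Objectives 3 to 5). Section 8.8, under Objective 2-5, presents the "SMD of each of the covariates for the comparison of drug users in the pre-RMM and post-RMM period as a measure of the impact"; the sentence continues by tying that impact to the profile of drug users.

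On precision, section 8.7 states that no sample size calculation was done, and then: "For Objective 3, 4 and 5, we expect an adequately large sample size to estimate Standardised Mean Differences (SMD) accurately". It adds that Objective 2 may be more limited because only 6 to 12 months of starters are used. Item 10.2 of the checklist in Appendix III, on whether study size or precision is estimated, is answered No with reference to 8.7.

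**The concern.** Directional hypotheses are paired with a single point measure, and nothing in the document shows how far that measure could move by chance. Objective 1, by contrast, specifies 95% CIs for its rates and prevalences. The document also goes further than silence: 8.7 makes a positive claim of accuracy with no figure behind it.

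Objective 4 is where this matters most, because it directly checks the restriction that high-dose products should no longer be first-line. It is also split by dose and indication. Without an interval, a chance shift in a small cell can be reported as a change in practice, and a real shift can be passed over as small.

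**Working it through.** **Is there a figure to reproduce?** No. The protocol gives no SMD precision, alpha, power or cut-off for Objectives 2 to 5. The one power statement in 8.7 concerns interrupted time series.

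**Inputs**
- Person counts and data locks: Table 3.
- Start of data: January 2010 (section 8.3), with 2012 for Belgium and 2017 for NAJS (section 11).
- Periods: pre up to October 2022, post from February 2023, three transition months left out (section 8.6.3). Section 11 drops the last six months of data only for Objectives 1 and 6, so all post months count here.
- Months (total / pre / post): Germany 165 / 154 / 8; Belgium 144 / 130 / 11; NAJS 82.5 / 70 / 9.5.

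**Assumption.** Group sizes are not in the document. I spread each Table 3 count evenly over the total months: n = count × months in period / total months.

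**Formula.** For a small SMD, SE = √(1/n_pre + 1/n_post), and the 95% half-width is 1.96 × SE.

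**Objective 4, whole cells**

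| Cell | n pre | n post | SE | 95% half-width |
|---|---|---|---|---|
| Belgium CMA (2,400) | 2,167 | 183 | 0.077 | 0.15 |
| NAJS NOMAC (1,900) | 1,612 | 219 | 0.072 | 0.14 |
| Belgium NOMAC (6,700) | 6,049 | 512 | 0.046 | 0.09 |
| Germany NOMAC (16,800) | 15,680 | 815 | 0.036 | 0.07 |
| NAJS CMA (15,300) | 12,982 | 1,762 | 0.025 | 0.05 |
| Germany CMA (173,900) | 162,307 | 8,432 | 0.011 | 0.02 |

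Example, Belgium CMA: 2,400 × 11/144 = 183; 2,400 × 130/144 = 2,167; √(1/183 + 1/2,167) = 0.077; 1.96 × 0.077 = 0.15.

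**Objective 4, strata.** The protocol gives no stratum shares. If a dose or indication stratum holds a quarter of users in both periods, SE doubles: 0.154 and 0.144, so half-widths of 0.30 (Belgium CMA) and 0.28 (NAJS NOMAC).

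**On the scale of proportions.** If the first-line proportion is near 0.5 (assumed), the standard deviation is 0.5. A half-width of 0.15 is then 0.15 × 0.5 = 7.5 percentage points, and 0.30 is 15 points.

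**Range.** Holding n_pre and changing n_post by a factor of two:
- Belgium CMA: 1.96 × √(1/92 + 1/2,167) = 0.21 if halved; 1.96 × √(1/366 + 1/2,167) = 0.11 if doubled.
- NAJS NOMAC: 1.96 × √(1/110 + 1/1,612) = 0.19 if halved; 1.96 × √(1/438 + 1/1,612) = 0.11 if doubled.

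**Objective 2, 6 months against 6 months.** All three data locks in Table 3 fall before the January 2024 end of the one-year window, so I used the 6-month version.
- Belgium CMA: 6 × 2,400/144 = 100 per period; 1.96 × √(2/100) = 0.28.
- NAJS NOMAC: 6 × 1,900/82.5 = 138 per period; 1.96 × √(2/138) = 0.24.

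**The case against.** **Descriptive study.** Objectives 3 to 5 are worded as description, and the SMD sentence is about the profile of users. That stands against any claim that a confirmatory test is missing. It does not remove the hypotheses in Tables 1 and 11, or the listing of the SMD as a main measure of effect.

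**A matter for the analysis plan.** Interval methods are often left to that document, which is not shown. This would answer a bare omission. It does not answer 8.7, where the protocol itself asserts accuracy without having estimated it.

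**Readers can compute intervals themselves.** Counts and proportions will be reported for Objectives 3 to 5, and aggregated data are available on request. This largely stands, except for cells below 5, which are masked. It does not help Objective 2, where medians and quartiles give no interval for the contrast.

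**Stronger readings that the documents do not support**
- A reader might infer that the sign of the SMD decides each hypothesis, so that with no effect the data would agree about half the time. No such rule is stated. Nor is one half general: for the rare meningioma history of Objective 3, simulation with identical periods put the chance of a lower post proportion anywhere from about 0.15 to 0.74, depending on assumed prevalence (0.001 or 0.0001) and group size.
- A reader might apply the half-widths above to all three objectives named in the 8.7 sentence. They rest on NOMAC or CMA starters. Objective 3 takes new users of any class of interest, for whom Table 3 has no count, and the Objective 5 period comparison also includes prevalent users. The figures bear on Objective 4, and separately on Objective 2.
- A reader might conclude that only CMA in Germany and NAJS is precise. NOMAC in Germany and in Belgium is reasonably precise too.
- A reader might treat the absence of an interval as peculiar to Objectives 2 to 5. The Objective 6 text names risk ratios without mentioning an interval either.

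**Conclusion.** The point holds in a limited form. The protocol fixes a point-only effect measure for hypotheses that have a direction, and it asserts accuracy for Objectives 3 to 5 with nothing estimated. For Objective 4 that assertion is doubtful in two of six drug-by-database cells, and more so in their dose and indication strata. In the other four cells it is reasonable overall. The imprecision of Objective 2 is real, but 8.7 already admits it.

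The sizes depend on the even spread over time and, for strata, on the quarter share. The Table 3 counts carry no restriction on age, sex or study period, so applying the entry criteria can only lower them; an uneven spread could move the result either way. The textual point does not depend on these assumptions. The documents do not show that any conclusion will be wrong, only that the planned output would not reveal how uncertain it is.

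**What to change.** In section 8.8 (Objective 2-5), Table 1 and Table 11, keep the SMD and add a 95% CI to each pre/post contrast:

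- Objectives 3 to 5: the difference in proportions with its CI.
- Objective 2: a CI for the SMD, or for a ratio of medians or geometric means, computed locally at each data partner.

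State that the hypotheses will be interpreted in light of these intervals. A formal rule that an interval must exclude no change is not needed in a largely descriptive study with many strata.

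In section 8.7, qualify the accuracy sentence for the smallest Objective 4 cells: CMA in Belgium, NOMAC in NAJS, and their dose and indication strata.

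The cost is protocol wording, a little more analysis code run locally within the federated design, and a less favourable statement of precision. No new data are needed.
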